8.3.2 Vital Signs

- Temperature, HR, RR, and BP will be assessed. The same method should be used for all measurements for each individual participant.
- HR and BP measurements will be assessed in a sitting position and should be preceded by a few minutes of rest.
- Vital signs are to be taken *after* completion of PROs and *before* blood collection for laboratory tests, except for Visit 2 (Randomization) where vital signs are collected before PROs as part of confirmation of eligibility.

8.3.3 Electrocardiograms

Single 12-lead ECG will be obtained and reviewed by an investigator or medically qualified designee (consistent with local requirements) as outlined in the SoA using an ECG machine that automatically calculates the HR and measures PR, QRS, QT, and QTc intervals. ECGs should be performed after the participant has rested quietly for at least 5 minutes. Refer to Appendix 10.3.2 for evaluation of potentially significant findings.

The investigator is responsible for retaining all copies of the ECG reports.

8.3.4 Clinical Safety Laboratory Assessments

Refer to Appendix 2 for the list of clinical laboratory tests to be performed and to the SoA for the timing and frequency.

- The investigator or medically qualified designee (consistent with local requirements) must review the laboratory report, document this review, and record any clinically relevant changes occurring during the study in the AE section of the CRF. The laboratory reports must be filed with the source documents. Clinically significant abnormal laboratory findings are those which are not associated with the underlying disease, unless judged by the investigator to be more severe than expected for the participant's condition.
- All protocol-required laboratory assessments, as defined in Appendix 2, must be conducted in accordance with the Laboratory Manual and the SoA.
- If laboratory values from nonprotocol-specified laboratory assessments performed at the institution's local laboratory require a change in study participant management or are considered clinically significant by the investigator (eg, SAE or AE or dose modification), then the results must be recorded in the appropriate CRF (eg, SLAB).

- For any laboratory tests with values considered clinically significantly abnormal during participation in the study or within 28 days after the last dose of study intervention, every attempt should be made to perform repeat assessments until the values return to normal or baseline or if a new baseline is established as determined by the investigator.

8.3.5 Pregnancy Testing

Pregnancy testing:

- Pregnancy testing requirements for study inclusion are described in Section 5.1.
- Pregnancy testing (urine and/or serum) should be conducted as per SoA at the specified visits during intervention. A negative pregnancy test should be confirmed prior to administration of study intervention.
- Additional serum or urine pregnancy tests may be performed, as determined necessary by the investigator or required by local regulation, to establish the absence of pregnancy at any time during the participant's participation in the study.

See Appendix 7 for country-specific requirements.

8.3.6 TB Testing

Participants will be screened for TB using the QuantiFERON Gold Test or equivalent as outlined in the TB screening eligibility criterion in Section 5.2. The QuantiFERON Gold Test or equivalent must be performed and read by trained and licensed personnel according to local guidelines. If this testing was performed at any site other than the investigator's facility, the results must be made available in written form as source documentation.

All participants must be evaluated for TB at Screening. The results of the TB screening must be interpreted in the context of the participant's epidemiology, history, exam findings, etc, and it is the responsibility of the investigator to determine if a participant has previous, active, or latent TB.

TB Testing

- The QFT should be performed at Screening on all participants unless the participant is considered to be TB test positive prior to Screening. The PPD skin test (also known as TB Skin Test or Mantoux Test) should be utilized when the QFT is not possible or if both tests are required per local guidelines. If local requirements dictate a local PPD be performed, this should be in addition to the QFT.
- Participants with documentation of prior positive results of QFT, PPD skin test, and/or history of latent or active TB are not required to repeat a TB test at Screening or during the study and should be considered TB test positive.
- If either PPD or QFT is positive, the TB test is considered positive.

- If the QFT or PPD skin test are performed within 90 days prior to Screening and source documentation is available, these tests do not need to be performed at Screening, provided nothing has changed in the participant's medical history to warrant a repeat test.
- If performed, the PPD should be read by a licensed healthcare professional between 48 and 72 hours after administration. A participant who does not return within 72 hours will need to be rescheduled for another skin test. The PPD skin test reaction will be measured in millimeters (mm) of induration and induration ≥ 5 mm is considered a positive reaction. The absence of induration will be recorded as "0 mm" not "negative."
- Participants who have had an ulcerating reaction to the PPD in the past should not be reexposed and the TB skin test should be considered positive.
- If the QFT is indeterminate, the site should perform a local QFT (or through the central laboratory if not locally available) to rule out a positive test result. If testing remains indeterminate or is positive, then the participant is considered to be positive for the purpose of this study. If the testing result is negative, then the participant is considered to be negative.
- If TB testing is done at Screening in participants considered at low risk for TB as described below and a positive result is reported, the procedure for "Interpretation of a positive TB test in low-risk participants" should be followed OR a prior treatment for latent TB is required.

Interpretation of a positive TB test in low-risk participants: In cases where the QFT by the central laboratory is positive and the investigator considers the participant at low risk for TB (ie, no risk factors identified on TB risk assessment questionnaire; see Appendix 10) and has no clinical suspicion of TB, the investigator may perform a local QFT (or repeat testing through the central laboratory if not locally available) to confirm the positive test result. If the repeat testing result is negative, the investigator may consider the test to be negative based on clinical judgment. If the repeat testing is positive or indeterminate, the test is considered positive.
- An equivalent interferon Gamma Release Assay such as T-SPOT TB test may be substituted for the QFT.
- TB test results will be retained at the site as the original source documentation.

Refer to the Laboratory Manual for any additional processing information and shipping instructions.

8.3.7 Chest X-ray

If permitted by the local health authority and IRB/EC, a chest x-ray will be obtained as outlined in the SoA to screen for TB (see exclusion criterion in Section 5.2). The chest x-ray must be focused on identifying abnormalities suggestive of TB. Posterior-anterior chest x-ray is recommended; however, local guidelines should be followed (see Appendix 7 for country-specific requirements).

The chest x-rays must be read and assessed by a medically qualified designee. Results must be within normal limits or not clinically significant for enrollment in the study. The investigator is responsible for retaining all source documentation.

8.3.8 HBV, HCV, and HIV Testing

Participants will be screened for HBV, HCV, and HIV as outlined in the SoA. See the HBV/HCV/HIV screening eligibility criterion (Section 5.2) to determine if further testing is needed or if the participant is eligible for the study. See Appendix 7 for country-specific requirements.

Hepatitis B

[figure not shown]
All participants will be tested for the presence of HBV at Screening using the following tests:

- HBsAg (hepatitis B surface antigen)
- HBcAb/anti-HBc (hepatitis B core antibody)

HBV serologic test results will be interpreted and managed as shown in [Figure 2](#).

- A positive result for HBsAg will be exclusionary.
- A positive test result for HBcAb requires HBV-DNA PCR testing (automatic reflex testing) (Scenario A):
 - HBV-DNA \geq LLOQ will be exclusionary
 - A participant with HBV-DNA $<$ LLOQ may be enrolled and the participant should have HBV-DNA testing performed approximately every 12 weeks (in correlation with a scheduled visit). If HBV-DNA is \geq LLOQ at any timepoint, the participant will require discontinuation of study intervention (Section 7.1).
- A negative test result for HBcAb does not require HBV-DNA PCR qualitative testing and the participant may be enrolled (Scenario B).

Figure 2 Interpretation and Management of HBV Serologic Test Results

DNA=deoxyribonucleic acid, HBcAb=hepatitis B core antibody, HBsAg=hepatitis B surface antigen, HBV=hepatitis B virus, LLOQ=lower limit of quantification.

^a These participants should have HBV-DNA testing performed approximately every 12 weeks (in correlation with a scheduled visit). If HBV-DNA is \geq LLOQ at any timepoint, the participant will require discontinuation of study intervention (Section 7.1).

See Appendix 7 for country-specific requirements.

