1.3.2 Blinded Extension Period

Study Period:	Blinded Extension Period										Notes
Visit Number/Title:	10*	11	12	13	14	15	TC	16	Discon	F/U TC	
Scheduled Day/Week	Wk 24	Wk 26	Wk 28	Wk 32	Wk 36	Wk 44	Wk 48	Wk 52		28 Days After Last Dose	
Day	169	183	197	225	253	309	337	365			
Recommended Window:	±7d	±3d	±3d	±7d	±7d	±7d	±3d	±7d		+7d	
Administrative Procedures											
Prior/concomitant medication		X	X	X	X	X	X	X	X	X	
IRT visit registration	X	X	X	X	X	X		X	X		
IRT rerandomization	X										
Collect participant identification card from the Double-Blind Treatment Period	X										
New participant identification card	X										Add rerandomization number to card at Visit 10. See Section 8.1.3.
Study intervention dispense/return	X	X	X	X	X	X		X	X		Assess compliance of returned syringe(s). Dispense at Wks 24 to 44; return at all visits.
Participant Reminder Log: train/dispense	X	X	X	X	X	X					For recording study intervention administration, any complaints/illnesses, and any new medications taken between study visits
Participant Reminder Log: review/collect		X	X	X	X	X	X	X	X		To be reviewed for accuracy. Verbal review at TC. See Section 8.1.9.5.
Dosing reminder telephone call							X				Last dose to be administered at Wk 50. Additional reminders as necessary per site.
Efficacy Procedures											PROs to be completed in order listed, before laboratory tests or other safety or efficacy procedures
VitiQoL Instrument					X			X	X		
VNS					X			X	X		
Patient Global Impression of Severity					X			X	X		
Patient Global Impression of Change/Meaningfulness					X			X	X		
Clinical Global Impression of Severity					X			X	X		
Clinical Global Impression of Change					X			X	X		

Study Period:	Blinded Extension Period										Notes
Visit Number/Title:	10*	11	12	13	14	15	TC	16	Discon	F/U TC	
Scheduled Day/Week	Wk 24	Wk 26	Wk 28	Wk 32	Wk 36	Wk 44	Wk 48	Wk 52		28 Days After Last Dose	
Day	169	183	197	225	253	309	337	365			
Recommended Window:	±7d	±3d	±3d	±7d	±7d	±7d	±3d	±7d		+7d	
F-VASI			X	X	X	X		X	X		
T-VASI					X			X	X		
CCI											
Other Procedures											
Photography (face)					X			X	X		
Photography (total body)					X			X	X		
CCI											
Safety Procedures											
Weight								X	X		
Vital signs		X	X	X	X	X		X	X		Taken after completion of PROs and before blood samples collection
Full physical examination								X	X		
Directed physical examination		X	X	X	X	X					Per institutional standards, consistent with local requirements.
Chemistry			X	X	X	X		X	X		

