Hematology		X	X	X	X	X		X	X		
Urinalysis (with microscopy)								X	X		To be performed at additional visits if clinical symptoms suggestive of UTI.
Local urine pregnancy test (POCBP only)			X	X	X	X		X	X		Administered predose. If urine test not confirmed as negative (eg, ambiguous result), serum test is required. See Appendix 7 for country-specific requirements.
HBV-DNA testing					X			X	X		Only for participants with positive HBcAb and HBV-DNA <LLOQ at Screening.
AE/SAE review		X	X	X	X	X	X	X	X	X	
PK/PD/Biomarkers (All participants)											
Blood for serum ADA								X	X		Samples for ADA and PK should be drawn at same time predose
Blood for serum PK								X	X		Samples for ADA and PK should be drawn at same time predose
Blood for DNA analysis								X	X		Leftover sample will be stored for FBR. See Section 8.9.

Study Period:	Blinded Extension Period										Notes
Visit Number/Title:	10*	11	12	13	14	15	TC	16	Discon	F/U TC	
Scheduled Day/Week	Wk 24	Wk 26	Wk 28	Wk 32	Wk 36	Wk 44	Wk 48	Wk 52		28 Days After Last Dose	
Day	169	183	197	225	253	309	337	365			
Recommended Window:	±7d	±3d	±3d	±7d	±7d	±7d	±3d	±7d		+7d	
Blood for immunophenotyping								X	X		See Section 8.7.2
Blood for serum biomarkers analysis								X	X		Leftover sample will be stored for FBR. See Section 8.9.
Blood for RNA analysis								X	X		Leftover sample will be stored for FBR. See Section 8.9.
ADA= antidrug antibodies; AE= adverse event(s); d= day; Discon= discontinuation; DNA= deoxyribonucleic acid; FBR= future biomedical research; F/U= follow-up; F-VASI= Facial Vitiligo Area Scoring Index; HBcAb= hepatitis B core antibody; HBV= hepatitis B virus; IRT= interactive response technology; LLOQ= lower limit of quantitation; PD= pharmacodynamics; PK= pharmacokinetics; POCBP= Participant of childbearing potential; Q2W= every 2 weeks; QoL= quality of life; RNA= ribonucleic acid; SAE= serious adverse event(s); SC= subcutaneous; TC= telephone call; TSH= thyroid-stimulating hormone; T-VASI= Total Vitiligo Area Scoring Index; UTI= urinary tract infection; CCI VitiQoL= Vitiligo Quality of Life Instrument; VNS= Vitiligo Noticeability Scale; Wk= Week. (a) Procedures for the Double-Blind portion of this visit are in Section 1.3.1 and should be completed before Blinded Extension procedures											

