5.2 Exclusion Criteria

An individual must be excluded from the study if the individual meets any of the following criteria:

(See Appendix 7 for country-specific requirements).

Medical Conditions

1. Has segmental vitiligo
2. Has $\geq 50\%$ leukotrichia on face or body
3. Has any other dermatological diseases that would interfere with vitiligo assessments
4. Has history of or current inflammatory condition other than vitiligo that, in the opinion of the investigator, could interfere with the evaluation of vitiligo
5. Has a known systemic hypersensitivity to IL-2, or modified IL-2 including MK-6194, or its inactive ingredients

Note: Refer to the IB for details regarding excipients for MK-6194.

6. Has a known history of hypereosinophilic syndrome or an eosinophil-related condition (eg, eosinophilic pulmonary disease including eosinophilic asthma, eosinophilic esophagitis, eosinophilic nephritis, eosinophilic granulomatosis with polyangiitis [formerly known as Churg-Strauss syndrome], etc)
7. Has an active or clinically significant infection requiring hospitalization or treatment with IV anti-infectives within 4 weeks prior to Randomization, or oral/intramuscular anti-infective therapy within 2 weeks prior to Randomization
8. Has symptomatic heart failure (New York Heart Association class III or IV) or myocardial infarction or unstable angina pectoris within 6 months prior to Screening
9. Has a severe chronic pulmonary disease requiring oxygen therapy
10. Has a transplanted organ, which requires continued immunosuppression
11. Has a history of any malignancy, except for successfully treated non-melanoma skin cancer or localized carcinoma in situ of the cervix
12. Is known to be infected with HBV, HCV, or HIV.
 - Participants with positive HBsAg are excluded from the study. Participants with negative HBsAg and positive HBcAb must have further testing for HBV-DNA. Participants with HBV-DNA \geq LLOQ are not eligible for the study.

Note: Participants with HBV-DNA <LLOQ are eligible and the participant should have HBV-DNA testing performed approximately every 12 weeks (in correlation with a scheduled visit).

- Participants with positive HCV antibodies at Screening must have further testing for HCV-RNA. Participants with HCV-RNA detectable are not eligible for the study. Participants with positive HCV antibodies, but HCV-RNA not detectable and successfully treated HCV with no recurrence for ≥ 1 year are eligible.

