- The participant has any malignancy, except for surgically removed and cured localized non-melanoma skin cancer or carcinoma in situ of the cervix.
- The participant is diagnosed with HBV, HCV, or HIV.
- The participant has HBV-DNA \geq LLOQ.

For participants who are discontinued from study intervention, but continue to be monitored in the study, selected visits and procedures, as outlined in the SoA and Section 8.10.5, should be completed.

Discontinuation from study intervention is “permanent.” Once a participant is discontinued from study intervention, they shall not be allowed to restart study intervention.

See Appendix 7 for country-specific requirements.

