8 STUDY ASSESSMENTS AND PROCEDURES

- Study procedures and their timing are summarized in the SoA.
- Adherence to the study design requirements, including those specified in the SoA, is essential and required for study conduct.
- The investigator is responsible for ensuring that procedures are conducted by appropriately qualified (by education, training, and experience) staff. Delegation of study-site personnel responsibilities will be documented in the Investigator Trial File Binder (or equivalent).
- All study-related medical (or dental) decisions must be made by an investigator who is a qualified physician (or dentist when appropriate).
- All screening evaluations must be completed and reviewed to confirm that potential participants meet all eligibility criteria. The investigator will maintain a screening log to record details of all participants screened and to confirm eligibility or record reasons for screening failure, as applicable.
- Procedures conducted as part of the participant's routine clinical management (eg, blood count) and obtained before providing documented informed consent may be used for screening or baseline purposes provided the procedures meet the protocol-specified criteria and were performed within the time frame defined in the SoA.
- Additional evaluations/testing may be deemed necessary by the investigator and or the Sponsor for reasons related to participant safety. In some cases, such evaluation/testing may be potentially sensitive in nature (eg, HIV, hepatitis C), and thus local regulations may require that additional informed consent be obtained from the participant. In these cases, such evaluations/testing will be performed in accordance with those regulations.
- The maximum amount of blood collected from each participant over the duration of the study will not exceed the volume mentioned in the Laboratory Manual.
- Repeat or unscheduled samples may be taken for safety reasons or for technical issues with the samples.

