8.10.3 Blinded Extension Period

The Blinded Extension Period begins with the participant's Week 24 administration of study intervention. Study procedures are outlined in Section 1.3.2. Participants who were assigned to the placebo group during the Double-Blind Treatment Period will be rerandomized to an active arm as outlined in Section 6.3.1.

Participants who permanently discontinued study intervention will continue to be monitored in the study according to the parameters outlined in Section 8.10.5.

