10.7.4 Country-specific Requirements for Japan

Section 1.3.1 Double-Blind Treatment Period

Study Period:	Screen	Double-Blind Treatment Period												Notes
Visit Number/Title:	1 Screen	2 Rand	3	4	5	TC	6	7	8	9	TC	10 ^a	Discon	
Scheduled Day/Week	Up to 4 wks	Day 1 Wk 0	Day 2	Wk 2	Wk 4	Wk 6	Wk 8	Wk 12	Wk12 +1d	Wk 18	Wk 20	Wk 24		
Day		1	2	15	29	43	57	85	86		141	169		
Recommended Window			±12h	±3d	±3d	±3d	±7d	±7d	±12h	±7d	±3d	±7d		
Safety Procedures														
HBV-DNA testing	X							X				X	X	Only for participants with positive HBcAb and/or positive HBsAb and HBV-DNA <LLOQ at Screening

Section 1.3.2 Blinded Extension Period

Study Period:	Blinded Extension Period										Notes
Visit Number/Title:	10 ^a	11	12	13	14	15	TC	16	Discon	F/U TC	
Scheduled Day/Week	Wk 24	Wk 26	Wk 28	Wk 32	Wk 36	Wk 44	Wk 48	Wk 52		28 Days after Last Dose	
Day	169	183	197	225	253	309	337	365			
Recommended Window:	±7d	±3d	±3d	±7d	±7d	±7d	±3d	±7d		+7d	
Safety Procedures											
HBV-DNA testing					X	X		X	X		Only for participants with positive HBcAb and/or positive HBsAb and HBV-DNA <LLOQ at Screening

Section 10.2

HBV Testing

Table Protocol-required Safety Laboratory Assessments

Other Screening Tests	• HBsAb
-----------------------	---------

[figure not shown]
HBsAb= hepatitis B surface antibody

Section 5.2: Exclusion Criteria and Section 8.3.8 HBV, HCV, and HIV Testing

12. Is known to be infected with HBV, HCV, or HIV:

- Participants with positive HBsAg are excluded from the study.
- For participants with positive HBsAb and negative HBcAb, HBV-DNA testing at screening is required. If HBV-DNA is \geq LLOQ, the participant must be excluded. If HBV-DNA is $<$ LLOQ, participant may be enrolled and HBV-DNA testing should be performed approximately every 12 weeks (in correlation with a scheduled visit) and at last scheduled visit. If subsequently, HBV-DNA is \geq LLOQ, the participant will require discontinuation of study intervention (Section 7.1).
- For participants with positive HBcAb and/or positive HBsAb and HBV-DNA is $<$ LLOQ at Screening, HBV-DNA testing should be performed approximately every 12 weeks (in correlation with a scheduled visit) and at last scheduled visit. If HBV-DNA is \geq LLOQ, the participant will require discontinuation of study intervention (Section 7.1).

HBV, HCV, HIV Testing

DNA=deoxyribonucleic acid, HBcAb=hepatitis B core antibody, HBsAg=hepatitis B surface antigen, HBV=hepatitis B virus, LLOQ=lower limit of quantification.

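### HBV-DNA is to be tested about every 12 weeks, but the global Extension schedule leaves 16 weeks (Week 36 to Week 52), so Week 36 is the last scheduled test that can stop dosing

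*Protocol*

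**What the plan says.** Protocol Section 5.2, criterion 12, admits HBcAb-positive participants whose viral DNA is not quantifiable, on a monitoring condition: "Participants with HBV-DNA <LLOQ are eligible and the participant should have HBV-DNA testing performed approximately every 12 weeks". Section 8.3.8 repeats the condition, "the participant should have HBV-DNA testing performed approximately every 12 weeks (in correlation with a scheduled visit", and so does the footnote to Figure 2. Section 7.1 lists HBV-DNA at or above LLOQ among the reasons for which study intervention must be discontinued.

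The global schedules turn this into marks. Section 1.3.1 has HBV-DNA at Screening, Week 12, Week 24 and the Discontinuation Visit. Section 1.3.2 has it at Week 36, Week 52 and the Discontinuation Visit, with the note "Only for participants with positive HBcAb and HBV-DNA <LLOQ at Screening". The same table states "Last dose to be administered at Wk 50", and Section 4.1 confirms that nothing is injected at Week 52.

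Section 8.10.3 says "Participants who were assigned to the placebo group during the Double-Blind Treatment Period will be rerandomized to an active arm", starting with the Week 24 dose. Section 8.10.2 requires the Week 24 double-blind procedures to be finished before that dose.

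The Japan appendix (Section 10.7.4) marks Week 44 as well. Its text is wider: "HBV-DNA testing should be performed approximately every 12 weeks (in correlation with a scheduled visit) and at last scheduled visit", and it also covers HBsAb-positive participants.

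**The concern.** The text promises a test about every 12 weeks, and the test carries a mandatory stopping rule. The global schedule keeps to 12 weeks three times and then goes to 16. Counting 12 weeks from Week 36 gives Week 48, which is only a telephone call. The on-site visits on either side are Weeks 44 and 52, each 4 weeks away. The schedule uses the later one, which falls after dosing has ended.

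What is at stake is the safety of a small subgroup. If viral DNA becomes quantifiable after the Week 36 sample, no planned test will show it in time to withhold an injection. Participants who received placebo first are worst placed, because their Week 12 and predose Week 24 samples come before any active drug.

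**Working it through.** **Inputs** (Protocol Sections 1.3.1, 1.3.2, 4.1 and 8.10). Visit days follow Day = 7 × week + 1: Week 12 = 85, Week 24 = 169, Week 36 = 253, Week 44 = 309, Week 48 = 337, Week 52 = 365. On the same rule Week 46 = 323 and Week 50 = 351. The windows at Weeks 36, 44 and 52 are ±7 days. All arms inject every 2 weeks, Week 0 to Week 50.

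**Reproducing the stated interval**
- Day 1 to 85: 84 days = 12 weeks.
- Day 85 to 169: 84 days = 12 weeks.
- Day 169 to 253: 84 days = 12 weeks.
- Day 253 to 365: 112 days = 16 weeks, and 112/84 = 1.33, so 33% longer.

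**Do the windows explain it?** With ±7 days at each end, a 12-week interval runs from 84 − 14 = 70 to 84 + 14 = 98 days. The scheduled gap runs from 112 − 14 = 98 to 112 + 14 = 126 days. The shortest scheduled gap equals the longest windowed 12-week gap. Longest against longest, 126/98 = 1.29.

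**Can the Week 52 result stop a dose?** The earliest Week 52 visit is Day 365 − 7 = 358, which is 358 − 351 = 7 days after the nominal last dose. It cannot. The Discontinuation Visit sample is taken once dosing has already stopped.

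**Scheduled on-drug tests able to stop dosing**
- Active from Week 0: Weeks 12, 24 and 36, so three.
- Switched from placebo at Week 24: Week 36 only, in the 26 weeks from first to last active dose.

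**Injections on or after the last such test.** The order of active and placebo injections in the Q4W arm is not stated. I assume active doses at Weeks 0, 4, …, 48.

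| | Now (Week 36) | With Week 44 added |
|---|---|---|
| Q2W from Week 0 (26 injections) | 8 (31%) | 4 |
| Q2W, placebo switchers (14) | 8 (57%) | 4 (29%) |
| Q4W from Week 0 (13 active) | 4 (31%) | 2 |
| Q4W, placebo switchers (7 active) | 4 (57%) | 2 (29%) |

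These counts include the injection given at the test visit itself. Strictly after the Week 36 test there are 7 Q2W injections (Weeks 38 to 50), or 7 of 14 in switchers. If active Q4W doses fell on the alternate weeks instead (26, 30, …, 50 in the Extension), switchers would still have 4 of 7.

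**How much of this is the mismatch?** A test at exactly Week 48 would have left 2 Q2W injections (Weeks 48 and 50) on or after it, and could have stopped Week 50 only. Under the Q4W assumption Week 50 is placebo, so no active dose would have been saved in that arm.

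**What a Week 44 test could stop.** Assay turnaround is not stated. From Day 309 the next injections are 14, 28 and 42 days away:
- result within 14 days: Weeks 46, 48 and 50;
- within 28 days: Weeks 48 and 50;
- within 42 days: Week 50.

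Under the Q4W assumption only Week 48 of these is active.

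**Number affected.** Not given. If 1% to 10% qualify (assumption), 165 × 0.01 = 1.65 and 165 × 0.10 = 16.5, so about 2 to 17 participants. For placebo, 55 × 0.01 = 0.55 and 55 × 0.10 = 5.5, so about 1 to 6.

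**The case against.** The strongest reply is that the text is advisory and approximate, and ties the interval to existing visits. Weeks 44 and 52 are equally far from Week 48, and Week 52 gives an end-of-treatment result. On this view the schedule is a permissible choice, and the avoidable exposure is much less than 57%: at most 3 Q2W injections, or 1 active Q4W injection under the stated assumption, and only if the result is back within 14 days. An exact 12-week test would have saved one Q2W injection at most. Cover also exists between tests. Chemistry is drawn at Weeks 36, 44 and 52, the stopping rule applies whenever a result appears, and Section 8 allows that "Repeat or unscheduled samples may be taken for safety reasons or for technical issues with the samples". The available safety summary reports no HBV signal. The prevalence range is assumed, and it ignores dropout and Japanese participants, who already have the Week 44 test. Finally, the proposed 8-week steps also differ from 12.

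Much of this stands as a limit on size. It does not remove the mismatch. The two candidate visits are equally distant in time but not equal in use, since only Week 44 can trigger the stopping rule during dosing. The gap reaches the longest windowed 12-week interval only at its own shortest. Unscheduled sampling needs a prompt, and the schedule, which Section 8 tells sites to follow, gives none. An 8-week step errs towards more monitoring, not less.

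**Conclusion.** The concern holds. Text and global schedule disagree by 4 weeks on a test that triggers mandatory discontinuation, and Week 36 is the last scheduled test that can act on dosing. For placebo switchers it is the only one while they are on active drug.

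The interval arithmetic rests on the Day rows alone, and the comparison of Week 52 with the last dose uses the nominal Week 50 day. The Q4W counts rest on an assumed dosing order, the benefit of a Week 44 test on an unstated turnaround, and the number affected on an assumed prevalence that is more likely too wide than too narrow a base. This is a participant-safety point for a small subgroup. It has no bearing on efficacy, power or Type I error. The Japan schedule is evidence that a Week 44 test is feasible; because its text is wider, it is not evidence of a contradiction.

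**What to change.** At the next amendment, mark HBV-DNA at Week 44 (Visit 15) in the global Section 1.3.2 row and keep Week 52. Nominal intervals from Week 0 become 12, 12, 12, 8 and 8 weeks, and the Week 44 result can still stop later doses. If 16 weeks is intended, state and justify that interval in Sections 5.2 and 8.3.8 and in the Figure 2 footnote.

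The cost is one mark in the table, one extra assay, and a slightly larger blood draw at a visit that already takes chemistry and hematology. It applies only to HBcAb-positive participants with HBV-DNA below LLOQ at Screening.
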